Data on congenital CMV infection among HIV exposed infants in sub-Saharan Africa are limited. A Kenyan study of infants born to mothers on perinatal Zidovudine, identified congenital CMV rates of 29% (4/14) in HIV-infected infants and 2.7% (1/37) in HIV exposed but uninfected infants. Zambian newborns admitted to a referral neonatal unit had a congenital CMV prevalence of 3.8% (15/395) whilst prevalence in HIV exposed newborns was 11.4% (9/79). Although HIV prevalence in South African pregnant women is one of the highest in the world (29.9%), a single study has evaluated the relationship between congenital CMV and HIV exposure. In Cape Town, Manicklal et al (2013) found a congenital CMV prevalence of 2.9% (22) in 748 HIV exposed babies. Maternal CD4+ count <200 cells/µL was independently

associated with congenital CMV. Clinical outcomes in these infants and prevalence of congenital CMV among HIV unexposed newborns were not investigated.

**Perinatal and Postnatal CMV infection:** Perinatal CMV infection is defined as CMV infection after 22 completed weeks (154 days) of gestation and seven completed days after birth. Postnatal CMV acquisition is CMV infection acquired any time after birth through consumption of breast milk from CMV seropositive, lactating mothers is common. Most term infants with perinatal CMV infection are asymptomatic, as maternally transferred CMV IgG antibody provides adequate protection against disease. However, studies have identified a significant risk for low-birth-weight (LBW), premature infants for the development of CMV disease such as pneumonia, hepatitis or sepsis-like illness. Data on severity and incidence of disease and long term impact in these infants is currently lacking requiring further study.

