**Current therapeutic options:** Treatment for maternal and newborn CMV infection is limited. Anti-CMV hyperimmunoglobulin is efficacious in preventing transmission from primary maternal infections but its value in secondary infection is uncertain. Some European countries offer universal maternal CMV screening or foetal anomaly ultrasonography to identify ventriculomegaly, intracerebral calcification and microcephaly. Foetal infection is confirmed by amniocentesis, not commonly available in LMIC, and women may be offered termination of pregnancy. Targeted CMV screening in symptomatic newborns and/or fail universal hearing screening occurs in the USA. Screening programmes have not been widely implemented due to lack of awareness, high costs and lack of rapid diagnostic tests. Ganciclovir (GCV) or Valganciclovir is administered to symptomatic CMV infected neonates, associated with improved audiologic outcomes. However GCV's effectiveness in asymptomatic cases has not been fully assessed. Both symptomatic and asymptomatic infants should be monitored regularly for neurological disability.

**Economic Impact:** The effect of congenital CMV disease on quality of life and cost to the health system led the Institute of Medicine (IOM) in the USA (1999) to declare development of a CMV vaccine as a highest priority. The IOM estimated that approximately \$1.9 billion per year is spent toward medical and educational costs for congenitally CMV infected children in the USA compared to costs of developing a CMV vaccine of \$360 million. The health economic implications of congenital CMV in low income countries is under-recognised or unknown.

**Impairment of immune response** The efficacy of infant vaccines in Sub-Saharan Africa has consistently been lower than in high income countries for a number of vaccines (e.g. measles vaccine, rotavirus vaccine). It has been postulated that CMV infection, due to its large recruitment of T-cells may have a role to play in modulating immune responses to infant vaccinations but only a few groups thus far have investigated this in children.

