## 2.2 Exploratory objectives

5. To explore the association between maternal CMV shedding in vaginal fluid and breast milk and the risk of congenital CMV infection assessed by quantitative CMV PCR.
6. Determine the incidence of postnatal CMV acquisition, in infants not CMV infected at birth, and explore possible risk factors, including maternal HIV status and the magnitude of maternal CMV shedding in vaginal fluid and breast milk.
7. Explore differences in immune responses to the primary and booster series of vaccinations (DTaP-Hib/HepB, PCV rotavirus and measles vaccines) between congenital CMV cases, postnatally acquired CMV cases and non-CMV infected controls at 6, 12 and 13 months of age.

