### 3.4 Objective 3, 6 (exploratory) and 7 (exploratory) Methods

[figure not shown]
***Study design:*** Prospective longitudinal cohort study of CMV infected and uninfected neonates

***Study participants:*** The cohort will consist of newborn infants identified as laboratory confirmed CMV infected from objective 2 forming the cases and a subset of neonates identified as CMV uninfected at birth chosen as controls. Each case will be matched to 2 controls by age, gestational age at birth ( $\pm 2$  weeks) and HIV exposure. Within 2 weeks of age, cases and controls will be recalled to the site to consent for follow up and initiation of investigations as illustrated in figure 2.

***Data collection:*** Postnatal CMV acquisition: A saliva and urine sample from each control infant will be collected at the 2 weeks visit. At subsequent follow up visits, infant saliva and urine will be collected from those that tested CMV negative at the preceding visit.

Incidence of neurological sequelae: neurological sequelae is one or more of: unilateral or bilateral SNHL, developmental deficit, unilateral or bilateral ocular abnormality, abnormal cerebral imaging, microcephaly, or seizures not related to an acute systemic infection or CNS insult (refer to [Appendix 11](#) for case definition of each sequela).

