Antibody to diphtheria toxoid, tetanus-toxoid, pertussis toxoid, filamentous hemagglutinin (FHA) and hepatitis B surface antigen (HBsAg) will be measured by an in-house Luminex multiplex immunoassay. Immune responses to the primary series of PCV will be measured by a standardized enzyme immunoassay (EIA) to test for vaccine serotype-specific capsular immunoglobulin (Ig) G antibody concentrations and opsonophagocytic assay. Titres of rotavirus-specific IgA will be determined in enzyme-linked immunosorbent assays. Refer to appendix 10 for the serological correlates of protection .

**Sample size:** The anticipated prevalence of neurological sequelae in CMV uninfected controls with uneventful foetal or perinatal periods is estimated at 1%. Prevalence of neurological sequelae in CMV infected infants is expected to be higher at approximately 17%. For 80% power, the difference that could feasibly be detected, is 17-fold i.e. 1% vs 17%. Allowing for a loss to follow up of 10%, 42 CMV infected infants and 84 controls (n=126) with an allocation ratio of 1:2 are required ([Appendix 9](#)).

**Data Analysis:** Table 3 describes the data analysis plan to determine the incidence and risk factors for neurological sequelae in congenital CMV infected infants

Table 3: Data analysis plan

Objective 3  Incidence calculation of one or more neurological sequelae for cases and controls at 2 weeks, 2 months, 6 months and 12 months of age dependent on investigations done at each visit  Comparison of proportions with permanent sequelae (hearing impairment and developmental deficit) at each visit between cases and controls using a Z test to compare ratios, including 95% confidence intervals.  Adjust for potential confounders (IUGR, symptoms at birth, gender and co-morbidities) by multiple logistic regression analysis to establish factors contributing to neurological sequelae.
Objective 6  Incidence of postnatal acquisition of CMV in newborns will be calculated at 2 months, 6 months and 1 year of chronological age. Incidence of neurological sequelae in postnatally infected infants will be calculated
Objective 7

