The magnitude of specific antibody response between cases and controls will be compared using the unpaired t test when data are normally distributed. In the scenario that the distribution is non-normal the Mann-Whitney test will be used instead. Normality will be tested using the Shapiro-Wilk test, where the assumption of non-normal data will be concluded based on a significant result. Frequency plots and P-P plots will also be used to confirm the normality assumption, or not.

Simple correlations will be assessed using Pearson or Spearman correlation in the case of normal or non-normal distribution, respectively. The resulting correlation coefficient will indicate the strength of association, whereas the significance test will provide the evidence of a linear correlation or not in the population.

**Potential challenges:** To account for loss to follow up and timely completion of investigations, a window period of 30 days is allowed from the date of each scheduled visit in which to perform the investigations. Transport costs will be reimbursed with R150 per scheduled visit and all investigations will be provided at no cost. Neurological sequelae in congenital CMV infected children may manifest beyond 12 months of age and long term follow up to 6 years is recommended. Hence, it is possible that this study may not detect all sequelae by 12 months of age and no differences may be observed between the 2 groups.

Parents may be reluctant to consent to a blood draw at 6 months of age and will be thoroughly counselled on the purpose and processing of the blood samples. The informed consent form has been amended to include the purpose of the blood draw and each mother will be given a new consent form to sign with the option of refusing to participate in the blood draw but continue with the rest of the study procedures.

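### Objective 7 names three CMV groups, but its stated test compares only two, so postnatally infected infants have no planned comparison and may sit among the controls

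*Combined protocol and SAP*

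**What the plan says.** Section 2.2 lists Objective 7 as exploratory and sets the comparison "between congenital CMV cases, postnatally acquired CMV cases and non-CMV infected controls at 6, 12 and 13 months of age". That is three groups.

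Section 3.4 covers Objectives 3, 6 and 7 with one cohort. Its cases are "newborn infants identified as laboratory confirmed CMV infected from objective 2 forming the cases". Its comparator is "a subset of neonates identified as CMV uninfected at birth chosen as controls", two per case, matched on age, gestational age and HIV exposure.

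For follow-up after the 2-week visit, section 3.4 says that "infant saliva and urine will be collected from those that tested CMV negative at the preceding visit". The analysis table uses the results for Objective 6: "Incidence of postnatal acquisition of CMV in newborns will be calculated at 2 months, 6 months and 1 year of chronological age", together with the incidence of neurological sequelae in infants infected postnatally.

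For Objective 7 the analysis text says: "The magnitude of specific antibody response between cases and controls will be compared using the unpaired t test" if the data are normal, and by Mann-Whitney otherwise. It adds simple correlations without naming the variables.

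**The concern.** The objective and the test do not match. A two-sample comparison of cases and controls cannot report on three groups, and nothing in section 3.4 says where an infant goes who was negative at birth and positive later.

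The plan's own background makes this more than a formality. Section 1.2 says that postnatal infection through "consumption of breast milk from CMV seropositive, lactating mothers is common", and the Objective 1 sample size in section 3.3 assumes 86% maternal seroprevalence. Section 1.2 also postulates that CMV infection, without restriction to congenital infection, "may have a role to play in modulating immune responses to infant vaccinations". If that is so, a control group fixed at birth is partly exposed to the factor under study. The congenital contrast would then be pulled towards zero, and the postnatal effect would not be estimated at all.

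**Working it through.** **Plan's own figure.** Objective 7 has no sample size or power statement. It uses the cohort sized for Objective 3: 42 cases and 84 controls, including a 10% allowance for loss. Evaluable numbers are 42 × 0.9 ≈ 38 and 84 × 0.9 ≈ 76.

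**Inputs assumed because the documents do not give them.**
- Effect of congenital infection: 0.6 SD, with SD = 1.
- Share of controls infected postnatally: q = 30%, 50% or 70%. The text says only that acquisition is common.
- Effect of postnatal relative to congenital infection: r = 1, 0.5, 0.25 or 0.
- Two-sided 5% test.

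**Expected contrast if controls are fixed at birth.** The control mean shifts by q·r times the congenital effect, so the expected difference is 0.6 × (1 − q·r). For q = 50% and r = 1 it is 0.6 × 0.5 = 0.30 SD. For q = 50% and r = 0.5 it is 0.6 × 0.75 = 0.45 SD.

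**Power of the two-group test.** I used the noncentral t with 112 degrees of freedom and noncentrality = difference / √(1/38 + 1/76) = difference / 0.199.

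**Power of congenital against never-infected.** The difference stays at 0.6 SD, but the comparator falls to 76 × (1 − q), that is 53, 38 or 23 infants. The standard errors are 0.213, 0.229 and 0.264.

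| | q = 30% | q = 50% | q = 70% |
|---|---|---|---|
| Two groups, r = 1 | 55% | 32% | 15% |
| Two groups, r = 0.5 | 72% | 61% | 50% |
| Two groups, r = 0.25 | 79% | 75% | 70% |
| Two groups, r = 0 | 85% | 85% | 85% |
| Congenital vs never-infected | 80% | 73% | 61% |

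Allowing for the larger variance of a mixed control group lowers the two-group figures by about two points at most.

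**Break-even.** The two approaches have about equal power when 1 − q·r equals the ratio of standard errors. At q = 30%, 0.199/0.213 ≈ 0.935, so r ≈ 0.065/0.3 ≈ 0.22. At 50%, 0.199/0.229 ≈ 0.866, so r ≈ 0.27. At 70%, 0.199/0.264 ≈ 0.752, so r ≈ 0.35. Above these values the three-group contrast has more power. Below them the two-group test does.

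**Postnatal against never-infected.** By normal approximation, the smallest difference detectable with 80% power is (1.96 + 0.84) × √(1/k + 1/m), where k controls are infected and m are not. For 23 and 53 infants it is 0.70 SD; for 38 and 38, 0.64 SD; for 53 and 23, 0.70 SD. Only large postnatal effects would be detected reliably, but the contrast would at least be estimated.

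**The case against.** Three objections have weight.

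First, the analysis text says only cases and controls. Objective 7 itself describes its comparator as non-CMV infected and lists postnatal cases separately, so *controls* may mean never-infected infants. The definition by status at birth may describe only how the shared cohort is enrolled. On this reading there is no dilution. This stands as an open reading, but it does not supply a comparison for the postnatal group.

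Second, section 3.2 refers to an appendix that summarises objectives, methods and analyses, and that appendix is not in the material available. A three-group analysis may be there. The point is therefore limited to what section 3.4 states.

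Third, the size rests on assumptions. A reader might infer that the difference shrinks by exactly the share of infected controls, or that a real effect will be missed. The documents do not support either. Proportional shrinkage needs r = 1, and CMV modulation of vaccine response is only postulated. At r = 0 nothing is lost, and if postnatal infection acted in the opposite direction the contrast would be exaggerated. At r = 0.25 the three-group contrast gains almost nothing at q = 30% and has lower power at 50% and 70%, because it removes infants from the comparator.

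**Conclusion.** The mismatch holds on the text: section 2.2 names three groups, and section 3.4 tests two. Under either reading of *controls*, the stated analysis does not answer Objective 7, because the postnatal group has no contrast.

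Dilution is conditional. It arises only if controls keep the birth definition, and its factor is (1 − q·r). Under the assumed inputs, power as written ranges from 15% to 85%, against 61% to 80% for congenital versus never-infected. These figures illustrate the dependence on q and r; they do not predict this study. It would be too strong to say that the plan does keep postnatally infected infants among the controls, since no sentence says so.

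The objective is exploratory, has no power claim of its own and supports no primary conclusion. Severity is minor to moderate.

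**What to change.** In the Objective 7 analysis of section 3.4, replace the two-sample test with one model of log antibody on three groups: congenital, postnatal and never-infected. Form the groups from the serial saliva and urine PCR already planned. Report congenital versus uninfected and postnatal versus uninfected, each with a confidence interval, adjusted for HIV exposure because it is a matching factor.

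State in advance when CMV status is assigned relative to vaccination. Section 3.4 places the primary doses at 6, 10 and 14 weeks and the blood draw at 6 months, while acquisition is assessed at 2 months and then at 6 months. An infection first detected at 6 months may therefore post-date the 14-week dose. One workable rule is to separate infection first detected by the 2-month visit from infection first detected at 6 months, with a sensitivity analysis using status at the blood draw. Also define *controls* explicitly for this objective.

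The cost is plan wording, with no new samples. The drawback is a smaller never-infected group, and hence some loss of precision for the congenital contrast if postnatal infection has little effect. Group sizes should be reported with the estimates.

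### Objective 7 compares individually matched infants with unpaired tests, so its intervals are somewhat too wide if the matching factors affect antibody level: a minor, cheaply fixed loss of efficiency

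*Combined protocol and SAP*

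**What the plan says.** One cohort serves Objectives 3, 6 and 7. Section 3.4 (Study participants) states: "Each case will be matched to 2 controls by age, gestational age at birth", within 2 weeks, and also by HIV exposure.

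The named between-group analyses, all in section 3.4 (Data Analysis), are:

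- **Objective 7 (exploratory):** the size of the antibody response "between cases and controls will be compared using the unpaired t test when data are normally distributed". Otherwise, "In the scenario that the distribution is non-normal the Mann-Whitney test will be used instead".
- **Objective 3:** proportions with permanent sequelae are compared "at each visit between cases and controls using a Z test to compare ratios, including 95% confidence intervals". A second step reads: "Adjust for potential confounders (IUGR, symptoms at birth, gender and co-morbidities) by multiple logistic regression analysis". No matching factor is in that list, and the model is not described as conditional.

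Section 2.2 frames Objective 7 as a comparison "between congenital CMV cases, postnatally acquired CMV cases and non-CMV infected controls at 6, 12 and 13 months of age", which is three groups. The analysis text names only cases and controls. No sample size, power, effect size or within-set correlation is given for Objective 7.

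**The concern.** Individual matching ties each case to its own two controls. Wherever the matching factors influence the outcome, infants in a set resemble each other more than infants from different sets. A test that treats all infants as independent puts that shared variation into its error term. The matching restricts which controls can be recruited, and its gain in precision is then not used.

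Changing the scale or switching to Mann-Whitney does not help, since both still assume independent samples. The stake is modest: wider intervals and some lost power for vaccine response, in a cohort whose case numbers are fixed by screening yield. A finding of no difference in Objective 7 would then be less informative than the data allow.

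**Working it through.** **Inputs from the plan**

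- 1:2 matching on age, gestational age and HIV exposure (section 3.4, Study participants).
- 42 cases and 84 controls, with 10% loss to follow-up (section 3.4, Sample size). 42 x 0.9 = 37.8, so about 38 sets if whole sets are lost.
- Expected case mix of 31 HIV-exposed and about 11 unexposed (section 3.3, Sample size).

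**Assumptions, because the plan is silent:** two-sided 5% level, a true difference of 0.5 SD, and a range for rho.

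**The plan's own figure.** Objective 7 has no power figure to reproduce. For Objective 3, the usual pooled two-sided formula at 17% v 1% with 1:2 allocation gives 33 cases (37 after loss), or 41 (46 after loss) with continuity correction, not 42. That is a separate matter; 42 is used here only to set the number of sets.

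**Step 1: variance of the case-control difference, n sets**

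- Assumed by the unpaired test: sigma^2 (1/n + 1/(2n)) = 1.5 sigma^2/n.
- True value: (sigma^2/n) [1 + (1 + rho)/2 - 2 rho] = 1.5 sigma^2 (1 - rho)/n.
- Ratio of standard errors, unpaired to true: 1/sqrt(1 - rho).

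**Step 2: power at 0.5 SD, 38 sets.** The unpaired standard error is sqrt(1.5/38) = 0.199 SD, and 0.5/0.199 = 2.52. With f = sqrt(1 - rho), the normal approximations are:

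- unpaired power = Phi((2.52 - 1.96)/f)
- matched power = Phi(2.52/f - 1.96)
- unpaired false-positive rate = 2[1 - Phi(1.96/f)]

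| rho | Interval too wide by | Unpaired false-positive rate | Power, unpaired v matched (normal approx.) | Power, unpaired v matched (simulated) |
|---|---|---|---|---|
| 0 | 0% | 5.0% | 71% v 71% | about 70% v 69% |
| 0.05 | 3% | 4.4% | 72% v 73% | about 71% v 73% |
| 0.1 | 5% | 3.9% | 72% v 76% | about 71% v 75% |
| 0.2 | 12% | 2.8% | 73% v 80% | about 73% v 80% |

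The last column simulates an unpaired t test against a test with matched-set effects. It agrees with the approximation to within about a point, or two for the matched test at rho 0, where estimating set effects costs a little.

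**Step 3: what would produce such a rho?** Only the matching factors can. Take HIV exposure alone, shifting antibody level by d SD. With the plan's case mix, (31/42)(11/42) = 0.193, so rho = 0.193 d^2/(1 + 0.193 d^2).

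- d = 0.5 gives 0.048/1.048 = 0.05.
- d = 0.75 gives 0.109/1.109 = 0.10.
- For rho = 0.2, d = sqrt(0.25/0.193) = 1.14.
- For rho = 0.5, d = sqrt(1/0.193) = 2.3.

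Gestational age can add to this. Age adds little, because infants are enrolled at birth and seen at common visit ages.

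**Step 4: Objective 3 at 17% v 1%.** With 38 sets and a set-level SD of 0.5, 1 or 2 on the logit scale, the Z test's standard error is too large by a factor of 1.002, 1.010 or 1.033. Power for the Z test against Mantel-Haenszel by set is 91.8% v 92.1%, 92.8% v 93.3% and 93.8% v 95.6%. A simulation with a different form of shared set effect gave at most about 3 points. Correlation is capped because control events are rare: its maximum at these rates is (0.01 - 0.0017)/sqrt(0.17 x 0.83 x 0.01 x 0.99) = 0.22.

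**The case against.** The strongest reply is that little is lost. Rho appears nowhere in the documents, and Step 3 shows that moderate effects of HIV exposure give only 0.05 to 0.10, worth about 2 to 4 points of power. Objective 7 is exploratory and unpowered, and the error is in the safe direction. In a matched cohort, ignoring the sets does not bias the crude comparison of risks. All of this stands, and it sets the grade.

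Two further replies stand in part.

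- **Unseen material.** Appendix 3, which summarises the analyses, was not available, and the wording of the Objective 3 logistic model does not exclude a conditional form. The Objective 7 tests, however, are named explicitly as unpaired.
- **Broken sets.** Controls who acquire CMV after birth move to a third group, so a strict paired test would fit poorly. This shapes the remedy rather than removing the point. With 42 sets at rho 0.2, a random-intercept model still gave 78% v 73% with 10% of infants missing and 68% v 62% with 25% missing. Reclassification to the third group was not modelled.

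A reader might infer a large loss, since at rho 0.5 power would be about 77% v 94%. The documents do not support that: HIV exposure alone would have to shift antibody level by about 2.3 SD. A reader might also infer that Objective 3 is seriously weakened. That would need a control rate well above the plan's 1%.

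**Conclusion.** The mismatch is real: matching is individual and the Objective 7 tests are unpaired. To the extent that HIV exposure and gestational age affect antibody level, the planned test is conservative and its interval too wide by 1/sqrt(1 - rho).

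Over a rho of 0 to 0.2 the cost runs from nothing to about 7 points of power, with intervals up to 12% too wide. This assumes a 0.5 SD difference, 38 complete sets and a two-sided 5% level, none of which the plan states for Objective 7. A larger rho would require very strong effects of the matching factors. For Objective 3 the gain is at most about 2 to 3 points at the plan's own rates.

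It would be wrong to say without condition that power is lost, or that the planned tests produce false positives. This is a cheap improvement and a minor efficiency point.

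**What to change.** **Objective 7.** Replace the unpaired t test and Mann-Whitney with a linear model of log-transformed antibody concentration or titre. Include infection group (congenital CMV, postnatally acquired CMV, uninfected) and a random intercept for matched set; the matching factors as covariates are an acceptable alternative. Keep infants from incomplete sets. Report the geometric mean ratio with its 95% confidence interval. Naming the log scale matters, because this change removes the plan's route for non-normal data.

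**Objective 3.** Use a Mantel-Haenszel comparison stratified by matched set, or add the matching factors to the logistic model.

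**Data.** Record the set identifier when controls are selected; it is harder to reconstruct later.

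**Cost.** Wording in the data analysis section and one variable in the dataset, with no extra infants, visits or samples. The downside is a slightly more complex model, with essentially no gain if rho is near 0.

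### Objective 7 antibody comparison: a Shapiro-Wilk pre-test on an unstated scale leaves no effect ratio with interval specified and no place for the matching factors

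*Combined protocol and SAP*

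**What the plan says.** Section 2.2 lists Objective 7 as exploratory. It asks for differences in vaccine response "between congenital CMV cases, postnatally acquired CMV cases and non-CMV infected controls at 6, 12 and 13 months of age". The laboratory part of section 3.4 names the endpoints: multiplex antibody levels, pneumococcal serotype-specific IgG with an opsonophagocytic assay, and rotavirus IgA ("Titres of rotavirus-specific IgA will be determined in enzyme-linked immunosorbent assays").

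The analysis text for Objective 7, after the data analysis table in section 3.4, reads: "The magnitude of specific antibody response between cases and controls will be compared using the unpaired t test when data are normally distributed". Then: "In the scenario that the distribution is non-normal the Mann-Whitney test will be used instead". The switch is a pre-test: "Normality will be tested using the Shapiro-Wilk test", "where the assumption of non-normal data will be concluded based on a significant result", with graphical support: "Frequency plots and P-P plots will also be used to confirm the normality assumption, or not".

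That text names no transformation, effect measure, confidence interval or covariate for the group comparison. Elsewhere the plan does: Objectives 1, 2 and 3 specify 95% confidence intervals, and Objectives 2 and 3 specify regression adjustment. Under the study participants paragraph of section 3.4, each congenital case is matched to two controls on age, gestational age and HIV exposure.

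**The concern.** Antibody concentrations and titres are usually right-skewed and are most naturally compared as ratios. A normality test on untransformed values of this kind will nearly always be significant at these sample sizes, so the written rule amounts to a Mann-Whitney test. That test gives a p-value, and the plan asks for nothing beside it. Neither candidate test accepts a covariate, so the matching factors play no part in the analysis.

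The stake is interpretability. Objective 7 has no sample size of its own and takes its group sizes from Objective 3, so many comparisons may be non-significant. Without an interval, a reader cannot tell whether a non-significant result excludes a meaningful reduction in response or is simply uninformative. Adjustment matters most where matching does not reach. The postnatally infected group is not matched, and the planned comparison is worded for cases and controls only. In addition, the potential-challenges paragraph of section 3.4 lets mothers refuse the infant blood draw while staying in the study, which can break matched sets for exactly this endpoint.

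**Working it through.** The plan gives no effect size, SD or power for Objective 7, so there is no figure of its own to reproduce.

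**Inputs from the documents.** Objective 3 sets 42 cases and 84 controls with 10% loss: 42 × 0.9 = 37.8 and 84 × 0.9 = 75.6, so about 38 and 76 evaluable.

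**Assumptions.** Log-normal values; log10 SD 0.1 to 0.7; two-sided alpha 0.05; Shapiro-Wilk at 0.05 in each group on untransformed values. None of these is in the documents.

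**1. What the rule selects, and what it costs in error rates.** Simulation, 2000 runs per setting, 38 vs 76. The ratio in each row is the one a log-scale comparison detects with 80% power.

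| log10 SD | Ratio | Normality rejected in at least one group | Type I error, planned rule | Power, planned rule | Power, t test on logs |
|---|---|---|---|---|---|
| 0.1 | 1.14 | 66 to 68% | 0.048 | 0.790 | 0.799 |
| 0.2 | 1.29 | over 99% | 0.052 | 0.776 | 0.794 |
| 0.3 | 1.47 | 100% | 0.052 | 0.777 | 0.786 |
| 0.5 | 1.90 | 100% | 0.044 | 0.770 | 0.785 |
| 0.7 | 2.45 | 100% | 0.048 | 0.779 | 0.805 |

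From SD 0.2 upward the rule is in effect Mann-Whitney. The power differences are 0.9, 1.8, 0.9, 1.5 and 2.6 points. A separate simulation with an assumed ratio of 0.6 and SD of the natural log between 0.8 and 1.2 (divide by 2.303: log10 SD 0.35 to 0.52) gave 88%, 70% and 54% for the planned rule against 89%, 73% and 56% on logs, a difference of 1 to 3 points.

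**2. What a log-scale analysis would report.** SE = SD × √(1/38 + 1/76) = SD × 0.1987. The 95% CI for the geometric-mean ratio is the estimate times or divided by 10^(1.96 × SE). The ratio detectable with 80% power is 10^(2.80 × SE).

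- SD 0.3: SE 0.0596; CI factor 1.31; detectable ratio 1.47.
- SD 0.5: SE 0.0993; CI factor 1.57; detectable ratio 1.90.
- SD 0.7: SE 0.1391; CI factor 1.87; detectable ratio 2.45.

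At SD 0.5 an effect well short of two-fold would often be missed, and only the interval would show what had been excluded.

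**3. What adjustment for HIV exposure changes.** If matching holds, crude and adjusted ratios agree (both about 1.00 in simulation with no true CMV effect). Suppose instead that 74% of one group and 55% of the other are HIV-exposed, and that exposure lowers log10 titre by h. The crude ratio is then 10^(−(0.74 − 0.55) × h). For h = 0.1, 0.2 and 0.3 this gives 0.96, 0.92 and 0.88, where the true ratio is 1. Simulation gave 0.97, 0.92 and 0.88, with the adjusted ratio staying at about 1.0. The imbalance and h are illustrations, not figures from the plan.

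**The case against.** **The scale is unstated, not stated as raw.** This stands. If log titres went through the same rule and were log-normal, both groups would pass in about 0.95 × 0.95 = 90% of samples. The t test would then run on logs, and its difference back-transforms to a geometric-mean ratio. Appendices 3 and 10, which are not in the supplied text, might settle the scale. The point is therefore conditional on untransformed testing, and the remedy includes stating the scale.

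**Little harm is done.** This also stands for error rates. A reader might infer inflated type I error or a material loss of power; the simulations show neither. A reader might also infer that HIV exposure would buy substantial precision, but nothing here quantifies such a gain.

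**Methods switching between antigens by chance.** A reader might infer this from any pre-test. It does not fit a rejection rate of about 100%: with the spreads considered plausible here, nearly every antigen takes the same route. A mixture on untransformed values needs a spread as narrow as log10 SD 0.1.

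**HIV exposure is matched.** True for congenital cases against controls, and it limits confounding there. It does not cover the postnatal group. Controls who acquire CMV leave the control group, and Objective 6 names maternal HIV status as a possible risk factor for that acquisition.

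**Mann-Whitney can be reported with medians or a Hodges-Lehmann interval.** It can, and the plan does not forbid it. It does not specify it either, and such a summary still takes no covariates.

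**The objective is exploratory.** Agreed. That limits the severity but does not reduce the need for an estimate.

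**Conclusion.** The point holds as a minor improvement to an exploratory analysis. If antibody values are tested untransformed and are roughly log-normal with log10 SD 0.2 or more, the rule selects Mann-Whitney in over 99% of samples at 38 vs 76. No effect ratio with interval is then specified, and gestational age and HIV exposure cannot be used. Validity is not at stake: type I error is 0.044 to 0.052 and power falls by only about 1 to 3 points.

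The documents do not support a claim that the plan commits to the raw scale, or that the matched congenital comparison is confounded by HIV exposure as designed. The value of adjustment lies with the unmatched postnatal group and with matched sets broken by refused blood draws; its size depends on imbalances and HIV effects that the documents do not give. The 38 and 76 are borrowed from Objective 3 and will be smaller if mothers decline the blood draw or controls become infected.

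**What to change.** Replace the pre-test rule for Objective 7 with one pre-specified model. At each age at which blood is drawn, fit a linear regression of log10 concentration or titre on CMV group (congenital, postnatal, uninfected), with HIV exposure and gestational age as covariates. Report each group contrast as a geometric-mean ratio, 10 to the power of the coefficient, with its 95% CI, for every antigen whether or not it is significant. State how infants are assigned to the postnatal group at that age. Pre-specify how values below the assay limit are handled, by imputation or as censored. Keep Mann-Whitney as a sensitivity analysis, where tied low values do less damage.

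The change uses data already planned for collection and alters no visit, sample or sample size. Its cost is the rule for low values, which a rank test largely avoids, and slightly more analysis work.
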